4.2. OTHER REPORTABLE INFORMATION

4.2.1. MEDICATION ERRORS

Medication error is defined as an error made in prescribing, dispensing, administration, and/or use of an investigational product.

Medication errors include, but are not limited to, the following:

- Administration of the wrong dosage to the subject (i.e., different from the dose prescribed by the protocol).
- Administration of study drug that has not been assigned to the subject.
- Administration of expired study drug.
- Administration by a route other than inhalation.
- Deviations to the study drug storage conditions when administered to the subject.
- Nasal cannula not removed.
- Air or oxygen tube not connected to the FOX-Flamingo inhalation system, damaged or kinked.
- Air or oxygen flow to the FOX-Flamingo inhalation system too low or too high.
- Re-use of inhalation set (i.e., the face mask, mask adapter, and nebulizer mesh/head and fill reservoir).

All medication errors that occur during the study should be reported to the Sponsor regardless of whether they are a cause of AEs/SAEs.

AE/SAEs resulting from medication errors need to be reported as any other AEs/SAEs (see section 4.1.2 and section 4.1.4) indicating the medication error.

For information on management of overdoses, please refer to section 3.3.4.3.

4.2.2. MEDICAL DEVICE ISSUES

All medical device issues that occur during the study should be reported to the Sponsor regardless of whether they are a cause of AEs/ SAEs.

AE/SAEs resulting from medical device issues need to be reported as any other AEs/SAEs (see section 4.1.2 and section 4.1.4) indicating the medical device issue.

5. STATISTICS

5.1. STUDY POPULATIONS

The following populations will be considered for analysis:

- **Modified Intent-to-treat (mITT) Population:** All randomized subjects who received at least 1 administration of study drug, as randomized (i.e., using the treatment to which the subject was randomized).
- **Safety Population:** All subjects who received at least 1 administration of study drug, as treated (i.e., using the treatment that the subject actually received).
- **PK population:** Subset of the subjects in the safety population for whom the primary PK data are considered to be sufficient and interpretable. For this study, this will correspond to all subjects in the safety population who received at least 1 administration of ALX-0171 and for whom at least three ALX-0171 serum concentrations have been determined.

The mITT Population will be the primary study population used for the analysis of efficacy data, the Safety Population for the analysis of safety, PD, and immunogenicity data, and the PK population for analysis of PK data.

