- s. All subjects will undergo PK analysis sampling (3 PK samples per subject), i.e., blood draws on Days 2-3: 1) pre-second dose, 2) between 0.5 hours and 3 hours post-second dose and at least 1 hour apart from the first sampling, and 3) between 3 hours and 6 hours post-second dose (and at least 1 hour apart from the previous sampling). If sufficient serum remains after PK assessment, exploratory biomarker (KL-6) may also be evaluated.
- t. If all hematology and biochemistry blood parameters required for the study are already known from analysis done as a routine assessment upon arrival at the hospital, collection of screening clinical laboratory samples does not need to be repeated for the purpose of this study. However, the samples should be analyzed at the same local laboratory that will be used for the remainder of the study.
- u. No blood sample needs to be taken in case of premature withdrawal from the study for subjects who did not receive any study drug.
- v. For subjects with a body weight below 5 kg and in case the blood volume needed for local clinical laboratory exceeds 2.5 mL, the sample for analysis of immunogenicity should not be collected at screening and on Day 14, but on Day 1 pre-dose and on Day 28, if possible.
- w. If sufficient serum remains after immunogenicity assessment, exploratory biomarker (KL-6) may also be evaluated. In case the blood sample for immunogenicity was not taken at screening, the sample should be collected at the Day 1 pre-dose time point, if possible.
- x. If sufficient serum remains after immunogenicity assessment, exploratory biomarker (KL-6) may also be evaluated. In case the blood sample for immunogenicity was not taken on Day 14, the sample should be collected at the EOS (Day 28) visit, if possible.
- y. An additional serum sample should be collected (if reasonably feasible) in case a serious and/or severe hypersensitivity reaction judged to be related to study drug occurs.

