3.6.4. PHARMACOKINETIC ASSESSMENTS

Systemic (serum) concentrations of ALX-0171 will be used as a surrogate for local (lung) concentrations.

A total of 3 blood samples for PK analysis are planned to be taken from each subject at the time points specified in the [Schedule of Assessments](#).

- pre-second dose,
- between 0.5 hours and 3 hours after completion of the second dose and at least 1 hour apart from the first sampling, and
- between 3 hours and 6 hours after completion of the second dose and at least 1 hour apart from the previous sampling.

Blood samples for PK analysis do not need to be collected in case study drug was not administered on Day 1 and/or Day 2.

The exact dates and times of blood sampling must be recorded.

If sufficient serum remains after PK assessment, exploratory biomarker (KL-6) may also be evaluated.

The blood samples will be collected from a vein, as using capillary blood (e.g., from heel pricks) is not allowed for PK assessments. Anesthetic cream or spray can be used to minimize the subject's discomfort and distress. For further details on sample collection, shipment, storage and processing, please refer to a separate Laboratory Manual.

Determination of ALX-0171 concentrations in serum will be done by a validated Ligand Binding Assay (LBA)-based method at a designated analytical laboratory according to the bioanalytical methodology and procedures described in a separate Bioanalytical Analysis Plan.

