3.6.10. TOTAL BLOOD VOLUME

Blood samples collected in this study will be used:

- i) for safety evaluation (clinical laboratory: hematology and clinical biochemistry),
- ii) to monitor the systemic concentration of ALX-0171 (as a surrogate measure of the local lung concentration), and
- iii) to assess potential immunogenicity ([Table 2](#)).

If all hematology and biochemistry blood parameters required for the study are already known from analysis done as a routine assessment upon arrival at the hospital, collection of screening clinical laboratory samples does not need to be repeated for the purpose of this study. However, the samples should be analyzed at the same local laboratory that will be used for the remainder of the study.

The blood samples for PK or ADA assessments will be collected from a vein, as using capillary blood (e.g., from heel pricks) is not allowed.

The precise assessments that are intended to be performed on each of the blood samples are arranged by priority; when insufficient volume is available (e.g., because of difficulties in or limits to obtaining blood), only the highest priority (-/ies) will be assessed (see [Table 2](#)).

Table 2: Timing, priority and estimated volume of scheduled blood draws

Sample	Priority	Maximal Target volume
1 blood draw at screening ^a	1. Clinical laboratory: - Hematology (whole blood) - Biochemistry (serum) 2. Immunogenicity (serum) ^b 3. Exploratory biomarker ^c	- whole blood for hematology (volume according to local practice) - whole blood to be processed into serum for biochemistry (volume according to local practice) - 1 mL whole blood, to be processed into serum for immunogenicity and biomarker ^b Total: 1 mL whole blood + volume needed for clinical laboratory
3 blood draws on Days 2-3	1. PK (serum) 2. Exploratory biomarker ^b	- 0.5 mL whole blood, to be processed into serum for PK and biomarker ^b Total: 1.5 mL whole blood
1 blood draw during the Day 14 FU visit	1. Clinical laboratory: - Hematology (whole blood) - Biochemistry (serum) 2. Immunogenicity (serum) ^b 3. Exploratory biomarker ^c	- whole blood for hematology (volume according to local practice) - whole blood to be processed into serum for biochemistry (volume according to local practice) - 1 mL whole blood, to be processed into serum for immunogenicity and biomarker ^b Total: 1 mL whole blood + volume needed for clinical laboratory

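### The PK population requires all three scheduled samples, so one missed draw discards an infant's other valid concentrations from a population PK analysis that could use them; the effect is modest and the fix is cheap

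*Protocol*

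**What the plan says.** Protocol 5.1 first describes the PK population in general terms, as safety-population subjects whose PK data are adequate and interpretable. It then fixes the criterion for this study: the subject received ALX-0171 at least once and is one "for whom at least three ALX-0171 serum concentrations have been determined". The same section assigns "the PK population for analysis of PK data".

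Protocol 3.6.4 states: "A total of 3 blood samples for PK analysis are planned to be taken from each subject". The times are before the second dose, 0.5 to 3 hours after it, and 3 to 6 hours after it. Footnote s of the Schedule of Assessments and Table 2 give the same count. No spare or replacement PK draw is provided for.

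Protocol 5.5 plans a population PK model by non-linear mixed effects, built on this study's serum concentrations and supplemented with data from ALX0171-C201 and other relevant studies. Individual CL/F, AUC and cumulative 72-hour AUC come from empirical Bayes estimation and are summarized by mean, SD and coefficient of variation. Section 5.5 states no minimum number of samples.

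The SAP, written for the abbreviated report after early termination, defines only the All Screened and Safety populations (4.1). Its PK output is a listing of concentrations and sampling times (Section 7, Listing 16.2.7.1) on the Safety Population. SAP Section 9 lists the analyses dropped from the protocol; neither the population PK model nor the PK population is among them.

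**The concern.** With three samples scheduled and three required, the threshold amounts to a complete-case rule. A child with two assayed concentrations and known times leaves the PK population because the third is missing. Mixed-effects models accept sparse and unequal profiles; this is a general property of the method, not a statement in the documents. The population definition therefore does not fit the planned analysis.

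The protocol foresees that draws may fail. On PK sampling it says: "The blood samples will be collected from a vein, as using capillary blood (e.g., from heel pricks) is not allowed for PK assessments". Section 3.6.10 provides for the case "when insufficient volume is available (e.g., because of difficulties in or limits to obtaining blood". The subjects are acutely ill children from 28 days of age and 3.0 kg.

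At stake is part of the first-listed objective, systemic PK. Each dose level has 12 planned active infants, and the trial stopped after one cohort. The sample size is partly justified by the precision of model-estimated PK parameters, with no stated allowance for missing samples.

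**Working it through.** **The plan's own figures.** 4 cohorts × 15 = 60 subjects; 15 × 4/5 = 12 active per cohort; 4 × 12 = 48 active in all; 3 draws × 0.5 mL = 1.5 mL in Table 2. These reproduce. The PK-precision basis of the 60 cannot be reproduced, because no coefficient of variation, precision target or missing-sample allowance is given.

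**Inputs.** Three samples per infant (3.6.4), three required (5.1), 12 active infants per cohort (3.1.1). The per-sample miss rate p is an assumption: 5%, 10% or 20%. How far misses cluster within an infant is also assumed, in three cases.

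**Share excluded by the all-three rule**

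- Fully clustered (all three samples missed or none): p.
- Intra-infant correlation 0.5 (beta-binomial with parameters p and 1−p): 1 − (1−p)(2−p)(3−p)/6. At p = 0.05 this is 1 − 0.95 × 1.95 × 2.95/6 = 0.089.
- Independent: 1 − (1−p)³. At p = 0.05 this is 1 − 0.95³ = 0.143.

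**Share a one-sample rule would bring back** (infants with two or one of three samples)

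- Fully clustered: 0.
- Correlation 0.5: p(1−p)(2−p)/2 + p(1+p)(1−p)/2. At p = 0.05 this is 0.046 + 0.025 = 0.071.
- Independent: 3p(1−p)² + 3p²(1−p). At p = 0.05 this is 0.135 + 0.007 = 0.143 (unrounded terms).

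**Expected infants of 12**

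| Assumed p | Clustering | Excluded by all-three rule | Recovered by one-sample rule | of which with two samples |
|---|---|---|---|---|
| 5% | full | 0.6 | 0 | – |
| 5% | 0.5 | 1.07 | 0.86 | 0.56 |
| 5% | none | 1.71 | 1.71 | 1.62 |
| 10% | full | 1.2 | 0 | – |
| 10% | 0.5 | 2.08 | 1.62 | 1.03 |
| 10% | none | 3.25 | 3.24 | 2.92 |
| 20% | full | 2.4 | 0 | – |
| 20% | 0.5 | 3.94 | 2.88 | 1.73 |
| 20% | none | 5.86 | 5.76 | 4.61 |

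**At least one of 12 excluded:** 1 − (1 − share excluded)¹². At 5% this is 46% (fully clustered) to 84% (independent); at 10%, 72% to 98%.

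**Valid data discarded, independent misses at 10%.** Of 12 × 3 = 36 planned concentrations, 36 × 0.9 = 32.4 are measured and 36 × 0.729 = 26.2 are used. The rule discards 1 − 26.2/32.4 = 19% of the valid measurements.

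**Who is recovered.** Two-sample infants make up 65/63/60% of those recovered at correlation 0.5, and 95/90/80% under independence, at p = 5/10/20%. If each sample is equally likely to be the one left, infants with only the pre-second-dose sample number at most 0.1/0.2/0.4 of 12.

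**The case against.** The strongest reply is that no output in the available documents is affected. The SAP has no PK population, and its listing shows every safety-population subject, including those with one or two concentrations. Whether partial profiles enter the model is for the separate PK analysis plan, which is not available, and SAP Section 7 plans only listings. This limits the impact. It does not remove the rule: Protocol 5.1 still assigns PK analysis to the complete-set population, and SAP Section 9 does not list the model as dropped.

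A second reply is that few samples should be missed. Inpatient stay is required on the treatment days, the post-dose windows are wide, each draw is 0.5 mL, and PK has first priority on these draws, so KL-6 is given up before PK when volume is short. This stands, and it makes the 20% row a high scenario.

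A third reply is that the model is supplemented with C201 data, so losing one or two sparse profiles matters less than a count out of 12 suggests. This also stands. The counts bear mainly on this study's individual CL/F and AUC summaries.

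A fourth reply is that complete sets are defensible for those summaries. Estimates from one sample shrink towards the population value and can understate the SD and CV. This is why the fix separates the model dataset from the summaries.

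A reader might also infer that any result below the quantification limit disqualifies an infant. The documents do not say so. Protocol 3.6.4 uses the same word for the act of assaying: "Determination of ALX-0171 concentrations in serum will be done by a validated Ligand Binding Assay". On the natural reading, a sample assayed as BQL has been determined; one line would confirm it.

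**Conclusion.** The point holds as a modest mismatch between Protocol 5.1 and 5.5. At least three means all three, and a single missed draw excludes an infant's remaining usable concentrations from the protocol's PK analysis set.

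The size rests on assumed miss rates. At 5% per sample the expected loss is 0.6 to 1.7 of 12 infants, and at 10% it is 1.2 to 3.3. Relaxing the rule recovers none of these if misses are fully clustered and nearly all if they are independent.

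A reader might go further and infer that the trial's reported PK results are compromised, or that several of the 12 infants will be lost. The documents do not support either. They record no miss rate, the SAP's listing does not use the rule, the model is supplemented from other studies, and the PK plan may define its own dataset. Confidence is medium. The change is worth making because it costs little.

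**What to change.** In Protocol 5.1 or the PK data analysis plan:

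- **Model dataset:** include every ALX-0171-treated subject with at least one assayed serum concentration taken after the first dose (the pre-second-dose sample counts) and known dosing and sampling times. State that BQL results count as determined.
- **CL/F and AUC summaries:** report the number of samples per subject and the shrinkage, and show the summaries both for all modelled subjects and for complete-set subjects.

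This takes a few sentences and no new data. The downside is greater shrinkage in estimates from one or two samples, which can understate the SD and CV; the paired summaries make that visible. The change does not recover infants with no PK samples, including those covered by this provision in 3.6.4: "Blood samples for PK analysis do not need to be collected in case study drug was not administered on Day 1 and/or Day 2".

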5.2. STATISTICAL AND ANALYTICAL PLAN

Analysis of all parameters will be described in a Statistical Analysis Plan (SAP) and a Data Analysis Plan (DAP; for PK analysis) and will comprise all methods applied for analysis of the corresponding data. There will be no interim analysis performed in this study.

The SAP and relevant analytical plans for PK, PD and immunogenicity will be generated under responsibility of the Sponsor, and will be finalised prior to database lock. Any deviations from the reporting and analysis plans will be reported in the Section of "Changes in the planned analysis" in the Clinical Study Report (CSR).

5.3. DEMOGRAPHICS AND BASELINE CHARACTERISTICS

Baseline characteristics will be summarized using descriptive statistics (including number of observations, mean, standard deviation, median, maximum, and minimum) for continuous variables and counts and percentages for categorical variables.

Prior and concomitant medications will be summarized by treatment group, by the number and percentage of subjects taking each medication, classified using World Health Organization (WHO) Drug Dictionary, anatomical therapeutic chemical (ATC) class and preferred term.

5.4. EVALUATION OF SAFETY

Safety and tolerability of ALX-0171 in Japanese infants and young children hospitalized for RSV LRTI will be evaluated based on the following:

- AEs will be fully described and coded according to the Medical Dictionary for Regulatory Activities (MedDRA) using the latest MedDRA version available at the time of database lock.
- A treatment-emergent analysis of AEs will be done.
- Frequency of subjects presenting with AEs, AEs leading to withdrawal, adverse drug reactions, and SAEs will be tabulated for each treatment group by system organ class and preferred term.
- For laboratory parameters, descriptive statistics (mean, median, standard error, minimum, and maximum) will be computed on the actual values and the change from baseline for each parameter. All laboratory values will be categorized according to their normal ranges as below, within or above normal.
- Other safety variables, including e.g., heart rate, need for oxygen therapy (and when applicable, relevant parameters such as duration of oxygen therapy needed, oxygen delivery mode, flow of inspired oxygen), or any significant worsening requiring immediate or intensive medical intervention, will be fully depicted using descriptive statistics.

Findings in physical examinations will be listed. Body weight and body temperature results will be summarized by descriptive statistics.

5.5. EVALUATION OF PK

Systemic (serum) concentrations of ALX-0171 will be used as a surrogate for local (lung) concentrations.

Individual study drug concentrations will be listed, e.g., in summary tables. In addition, a listing of the actual sampling times relative to the study drug administration times will be presented. If considered meaningful, geometric means and standard deviations will be added to the summary tables.

A population PK model (non-linear mixed effect modeling) will be developed based on the ALX-0171 serum concentrations from this study. The dataset will be supplemented with serum concentration data from Study ALX0171-C201, and any other studies that are

considered relevant to support model structure. The covariate analysis will include the investigation of ethnicity.

Individual PK parameters will be derived by means of empirical Bayesian estimation. The following individual PK parameters will be provided: apparent clearance (CL/F), area under the curve (AUC) as nominal (filling) dose divided by CL/F and cumulative AUC over 72 hours as an expression of the cumulated exposure during the course of treatment.

Individual PK parameters will be summarized with sample size, mean, standard deviation and coefficient of variation.

The modeling exercise will be described in a separate analysis plan and will be reported in a separate report. The main findings will be summarized in the CSR.

5.6. EVALUATION OF ANTIVIRAL EFFECT

The antiviral effect (viral load in samples from nasal swabs) parameters will be analyzed using descriptive statistics. The data will be listed and summarized in tabular and/or graphical form.

The viral load (as assessed by plaque assay and qPCR) will be characterized through parameters including time-to-below the limit of quantification (BQL), time-to-undetectability, time-weighted average change from baseline up to Day 3 and Day 14, number and percent of subjects with undetectable RSV (from Day 1 to Day 14), number and percent of subjects with BQL and change from baseline in viral load.

5.7. EVALUATION OF CLINICAL ACTIVITY

Based on the Clinical Activity Outcome Measures, the following composite scores will be calculated and summarized descriptively:

- RDAI score (based on wheezing and respiratory muscle retractions, see [Appendix 1](#)),
- RACS; based on RDAI and change in respiratory rate),
- Global Severity Score (based on respiratory parameters, medical interventions, feeding, general appearance and body temperature).

The feeding and oxygen saturation outcome measures will be used to calculate Time-to-Clinical Response. Kaplan-Meier estimates will be provided.

Subjects will be considered to have met the Clinical Response criteria when both of the following criteria are fulfilled:

- Stable oxygen saturation on room air, defined as $\text{SpO}_2 \geq 95\%$ over a period of at least 4 hours to allow for hospital discharge.
- Adequate oral feeding which is sufficient to maintain hydration and to allow for hospital discharge, in the judgment of the Investigator.

5.8. EVALUATION OF IMMUNOGENICITY

Immunogenicity will be evaluated systemically in serum. Individual immunogenicity results will be listed, and summarized using descriptive statistics.

Prevalence of pre-Ab and incidence of TE ADA or NAb, as well as titer levels (TE ADA) and normalized ratios (NAb) of the antibody responses, will be reported.

Potential correlation between pre-Ab, TE ADA or NAb and safety, PK or efficacy will be assessed.

In case of severe and/or serious hypersensitivity reactions judged to be related to study drug occurs, a blood sample will be collected to further characterize the hypersensitivity reactions (if deemed necessary). Correlation between hypersensitivity reactions and immunogenicity results will be assessed. Results will be summarized through listing of the individual results.

5.9. EVALUATION OF PD

The PD characteristics (serum levels of KL-6) will be analyzed using descriptive statistics. The data will be listed and summarized in tabular and/or graphical form.

